## **Study Information from <https://osf.io/rh9ps>**

### **Title**

Kindergarten Children Acquiring Words through Storybook Reading (DC012824), Study 3

### **Research Questions**

3.1. What amount of testing during treatment (low, medium, high): (a) enhances learning during treatment and/or (b) reduces forgetting post-treatment? 3.2. What pre-treatment characteristics of kindergarten children with Developmental Language Disorder (DLD) are associated with (a) learning during treatment and/or (b) forgetting post-treatment? 3.3. At what point (a) during treatment can learning outcomes be accurately predicted; and (b) during post-treatment monitoring can retention outcomes be accurately predicted?

### **Hypotheses**

3.1. (a) Lower testing during treatment will lead to steeper positive slopes during treatment than higher testing. The exact pattern of the treatment conditions is not predicted (e.g., low and mid better than high versus low better than mid and high versus low better than mid better than high) (b) Higher testing during treatment will lead to smaller negative slopes (i.e., less forgetting) post-treatment than lower testing. The exact pattern of the treatment conditions is not predicted (e.g., high and mid better than low versus high better than mid and low versus high better than mid better than low). 3.2. (a) Higher language (specifically vocabulary and narrative skills), working memory, and/or episodic learning scores will be associated with steeper positive slopes during treatment. (b) Better treatment learning and/or decay scores will be associated with smaller negative slopes post-treatment, indicating less forgetting. 3.3. (a) Accuracy in predicting learning outcomes will increase at each treatment point, and there will be a point during treatment when outcomes can be accurately predicted. The specific earliest point in treatment (reading 1, 2, 3, 4, or 5) when accurate predictions can be made is unknown without any specific hypothesis. (b) Accuracy in predicting retention outcomes will increase at each post-treatment point, and there will be a point during post-treatment when outcomes can be accurately predicted. The specific earliest point in post-treatment (immediate, 4-week, 8-week) when accurate predictions can be made is unknown without any specific hypothesis.

### **Sampling Plan**

#### **Existing Data**

Registration prior to creation of data

Explanation of existing data

N/A -- Not using existing data

Data collection procedures

See attached file for details.

- [Data collection procedures.pdf](#)

Sample size

Sixty kindergarten children with DLD will participate. Children will be randomized to one of the 3 treatment manipulations (see manipulated variables) yielding 20 children per treatment condition. For each child definition and naming data will be collected for 30 treated words and 30 control words: 1 time pre-treatment, 6 times during treatment (repeated book readings 1-6), and 4 times post-treatment (immediate, 4-weeks, 8-weeks, and 12-weeks post-treatment).

Sample size rationale

3.1. Power Analysis for Research Question 3.1. Monte Carlo studies were conducted using Mplus to determine power to detect treatment differences in slope across 7 (treatment) or 5 (retention) data points. Slope reliabilities of .6 and .8 were considered in the specification of the population parameters. Both linear growth models and latent basis models with nonlinear growth were examined given that the expected shape of the trajectories is uncertain. Intraclass Correlation Coefficients (ICCs) from our prior studies indicated that between 10% and 30% of the variance in word learning was between persons. Thus, ICCs of both .10 and .30 were used in the power analysis. We will have .80 power or greater to detect moderate slope differences ( $d = .5$ ) between two groups of 20 individuals in the treatment phase with 7 data points. In the post-treatment phase, with 5 data points, we will have .80 power to detect slightly larger slope differences ( $d = .6$ ). Attrition has been minimal (1.9%). Thus, we will recruit additional children, as needed, to replace any children who do not complete the study. We will check the assumptions used in our power analysis yearly and update target sample size to maintain power. 3.2. Power Analysis for Research Question 3.2. Additional Monte Carlo studies were conducted using the same software, intraclass correlation coefficients, and slope reliabilities as for RQ3.1. Prior research by the team has indicated that correlations between predictors and learning are in the range of .4 and .5. Power to detect the relationship between level two predictors of this magnitude and slopes added to the treatment model will range from .70 to .85. Power to detect the main effect of each covariate at the last treatment point will similarly range from .73 to .87. Although power appears sufficient with a sample size of 60, an alternative approach if power is insufficient is to loosen our criteria for statistical significance and search for “promising” key moderators. Promising key moderators would need further testing as the

development of this treatment moves forward but would inform our understanding of which children with DLD may benefit from the treatment, addressing the research question. 3.3 There is no specific power analysis for research question 3.3.

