#### Stopping rule

Power estimates based on simulations indicate that a total of 60 participants will be needed to detect the expected effects. Because we are interested in outcomes that are assessed one year after treatment, and there is minimal risk to treatment participation, we will not stop study recruitment until we have reached our recruitment goal.

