## Analysis Plan

### Statistical models

Research Question 3.1: We will use a multi-level modeling approach for (a) learning during treatment (7 observations: pre-treatment, repeated readings 1-6); (b) post-treatment forgetting (5 observations: reading 6, immediate, 4-week, 8-week, 12-week post). We will examine definition and naming data separately, yielding four models: treatment definition, treatment naming, post-treatment definition, post-treatment naming. For each model, observations at each test (level 1) are available for each participant (level 2). The expected shape of the trajectories is not known so the analytic approach will use either linear growth modeling or latent basis modeling, depending on which is most appropriate. Participants are randomly assigned to treatment (low, mid, high testing), and treatment will be included in the model as a fixed factor at level 2. The dependent variable is number of words correct. This count variable will likely not fit a normal distribution, and thus, an appropriate link function, such as a Poisson distribution, will be used. The research aim is to detect

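### The power statement for RQ3.1 does not define d; in between-child slope-SD units the stated .80 is not reproduced, and .80 power needs about 1.0-1.2 slope SDs

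*Combined protocol and SAP*

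**What the plan says.** Under Sample size rationale, item 3.1, the plan reports Monte Carlo studies in Mplus for treatment differences in slope over 7 (treatment) or 5 (retention) points. The two claims are "We will have .80 power or greater to detect moderate slope differences ( $d = .5$ ) between two groups of 20 individuals" and, for the post-treatment phase, "we will have .80 power to detect slightly larger slope differences ( $d = .6". The word moderate is attached to d = .5 only; d = .6 is described as slightly larger.

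The inputs given are ICCs of .10 and .30 and the following: "Slope reliabilities of .6 and .8 were considered in the specification of the population parameters". As to the form of the growth curve, the plan reports that more than one was tried: "Both linear growth models and latent basis models with nonlinear growth were examined". No denominator or time unit is given for d, and no alpha or sidedness. Inference criteria names likelihood ratio tests without a significance level.

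Statistical models, Research Question 3.1, says "treatment will be included in the model as a fixed factor at level 2", with all pairwise condition contrasts tested on the slope. The Stopping rule relies on the simulations: "a total of 60 participants will be needed to detect the expected effects". The Sample size rationale adds "We will check the assumptions used in our power analysis yearly and update target sample size to maintain power". For RQ3.2 it states that power for covariates correlated .4 to .5 with learning and "slopes added to the treatment model will range from .70 to .85".

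**The concern.** Treatment varies between children, so each pairwise contrast compares 20 independent children with 20. More test occasions make each child's slope more precise, but they do not add children. A standardised difference of .5 between two groups of 20 ordinarily has power of about one third, so .80 or more for a moderate slope difference needs an explanation. The likeliest one is that d is not in slope-SD units, and the text does not say.

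The total of 60 and the yearly review of power both rest on this statement. A reader who takes d as a conventional standardised difference between children's slopes will believe the study is well placed to detect moderate differences, and may read a null result as evidence against them.

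**Working it through.** **Inputs from the plan:** 20 per group; 7 or 5 points; slope reliability (rel) .6 or .8; ICC .10 or .30; 30 treated words per child. **Assumed:** two-sided .05, complete data, equal spacing, noncentral t with 38 df (57 df if the third arm contributes to the variance).

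**1. Slope-SD units.** The observed-slope SD is the true-slope SD divided by √rel. The standardised contrast is therefore δ = d√rel, with noncentrality δ√(20/2) and critical t 2.024.

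| d | rel | δ | noncentrality | power, 38 df | power, 57 df |
|---|---|---|---|---|---|
| .5 | .6 | .387 | 1.22 | .223 | .226 |
| .5 | .8 | .447 | 1.41 | .281 | .285 |
| .5 | 1 | .500 | 1.58 | .338 | .343 |
| .6 | .6 | .465 | 1.47 | .299 | .304 |
| .6 | .8 | .537 | 1.70 | .380 | .385 |
| .6 | 1 | .600 | 1.90 | .456 | .462 |

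The stated .80 is not reproduced. One-sided .05 with perfect reliability gives only .46 and .59 (38 df).

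The result does not depend on the t approximation. In slope-SD units, simulated free-loading latent basis models (likelihood ratio test, 1,500 runs per cell) gave .225-.296 and .299-.403. Simulated Poisson models with random intercept and slope (2,000 runs per cell; assumed means 2 to 10 words in treatment and 10 to 6 after, intercept SD .4) gave .248-.310 and .317-.411.

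**2. Difference detectable with .80 power.** With 38 df, .80 power needs δ = 0.909. In true-slope SDs this is 0.909/√.8 = 1.02 and 0.909/√.6 = 1.17. It depends on reliability and n, not on the ICC or the scale of d.

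**3. Cross-check against RQ3.2.** Power is approximately Φ(atanh(r√rel)·√(N−3) − 1.96).
- N = 60, r = .4: .68 (rel .6) and .81 (rel .8). For r = .5: .87 and .95. These are broadly in line with the plan's .70-.85, so slope-SD units fit RQ3.2.
- On the same scale d = .5 is r = .5/√(.5² + 4) = .243. With N = 40, power is .21 and .27. If both items use one scale, RQ3.1 claims at least .80 for about half the correlation in two-thirds of the children.

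**4. Other scales.** Set intercept-plus-residual variance to 1, residual variance σ² = 1 − ICC, and Sxx = 28 (7 points) or 10 (5 points). Slope variance is rel/(1−rel)·σ²/Sxx, and observed-slope variance is σ²/[Sxx(1−rel)]. The intercept sits at the first point of the phase, with no intercept-slope covariance (assumed).
- *Per interval over total SD:* δ = d / observed-slope SD.
- *Whole phase over end-of-phase SD:* δ = d·SDend/(T × observed-slope SD), where T = 6 or 4 and SDend² = ICC + σ² + T² × slope variance.
- *The same with a per-word ICC:* σ² = (1 − ICC)/30.

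Each cell gives 7 points, d = .5 / 5 points, d = .6:

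| ICC | rel | power, per interval | that d in slope SDs | power, whole phase, per-occasion ICC | power, whole phase, per-word ICC |
|---|---|---|---|---|---|
| .10 | .6 | 1.00 / .97 | 2.28 / 1.63 | .32 / .41 | .58 / .67 |
| .10 | .8 | .97 / .79 | 1.39 / 1.00 | .33 / .43 | .46 / .57 |
| .30 | .6 | 1.00 / .99 | 2.58 / 1.85 | .35 / .44 | .93 / .96 |
| .30 | .8 | .99 / .88 | 1.58 / 1.13 | .34 / .45 | .75 / .84 |

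Example for the first row at 7 points: slope variance is (.6/.4)(.9/28) = .0482, so the slope SD is .220 and d = .5 per interval is .5/.220 = 2.28 slope SDs.

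The per-interval scale also fits the step from .5 to .6 between phases: d = .5 with 5 points gives only .63-.96. If the post-treatment tests sit at 0, 0, 4, 8 and 12 weeks and d is per 4 weeks, d = .6 gives .62-.95.

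Expressed in end-of-phase SDs, the difference detectable with .80 power is about 0.9-1.0 with a per-occasion ICC and about 0.4-0.8 with a per-word ICC.

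**The case against.** The strongest reply is that an undefined d is not a wrong d. The population values and alpha are not in the documents, and the per-interval scale essentially gives both stated power figures. That stands: a reader might infer that the Mplus runs are in error, and the documents do not support it.

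A second reply concerns the ICC. The plan speaks of variance in word learning, with 30 words per child, so a per-word ICC is a plausible reading. At ICC .30 and reliability .6 a whole-phase d of .5 over the end-of-phase SD then has power .93, and d = .6 passes .80 in both ICC .30 cells. A reader might infer that no scale reconciles the power with the label, or that only large differences are detectable. Neither follows on the end-of-phase scale. What survives is narrower: at ICC .10 this reading still fails, and wherever .80 is reached the difference is at least about 1 slope SD (1.43 in the .93 cell).

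Third, the study team may hold the simulation inputs, so the documents do not show that the yearly check cannot be run. They show only that a reader cannot tell what target it would maintain.

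**Conclusion.** The concern holds as an undefined effect size with consequences for how the power is read. In between-child slope-SD units, the scale that fits the plan's own RQ3.2 figures, power is about .22-.29 for d = .5 and .30-.39 for d = .6, against a stated .80 or greater and .80. Scales that deliver the stated power exist, but under a normal linear model .80 power with 20 v 20 corresponds to a difference of about 1.0-1.2 slope SDs (reliability .8-.6), however d is expressed. Whether that is moderate at the end of the phase depends on how the ICC is read.

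These figures assume two-sided .05, no multiplicity adjustment and complete data. The scale comparisons also assume equal spacing and no intercept-slope covariance. A reader might infer that the trial needs several times more children, since slope-SD units would call for 80-106 per group at d = .5 and 56-74 at d = .6. The documents do not establish that, because they do not say d is on that scale. This should be corrected, but it is not a reason to hold the study.

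**What to change.** Retrieve the Monte Carlo population values, or rerun the simulations if they cannot be found. In Sample size rationale, item 3.1, state the SD and time unit of d, the alpha, the sidedness, and whether the ICC is per occasion or per word. Then:

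- If d is in slope-SD units, restate the power at d = .5 and d = .6.
- Otherwise, drop or qualify the word moderate and give the implied differences in slope SDs and end-of-phase SDs.
- In either case, state the difference detectable with .80 power (about 1.0-1.2 slope SDs at reliability .8-.6), and say whether the d of RQ3.1 and the r of RQ3.2 share a slope scale.
- Use the same definition in the Stopping rule and in the yearly power check.

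The cost is wording, plus a rerun only if the inputs are lost. The restatement needs no added enrolment. The downside is a less favourable stated power or effect label.

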differences between treatment conditions, therefore all possible pairwise comparisons will be conducted rather than an omnibus test. The slope by treatment condition interaction will be the effect of interest in determining whether there is differential learning or forgetting across low, mid, high testing. While the focus of our analyses is on treated words, a similar modeling approach will be used to model any learning of control words during treatment. We expect relatively flat trajectories for control words in all three treatment conditions and this will allow for inferences to be made about the effect of treatment rather than development or maturation Research Question 3.2: We will add pre-treatment measures as covariates to the models used in RQ3.1 to examine the relationship between these covariates and (a) learning slopes during treatment and (b) forgetting slopes post-treatment. Recall that there are several skills relevant for learning (language, attention, working memory, episodic learning) and forgetting (treatment learning, decay) and that we have multiple measures to tap different aspects of each skill (see measured variables table). Likewise, we also will examine biological and environmental variables as predictors. Previous research has indicated that the test measures are moderately correlated at around  $r = .50$ . Since these measures are theoretically and mathematically distinct (which we will confirm via correlations), we will examine the effect of each of these predictors individually. We hypothesize that higher language, attention, working memory, and/or episodic learning scores will be associated with steeper slopes during treatment. Similarly, we hypothesize that better treatment learning and decay scores will be associated with smaller slopes, indicating less decline post-treatment. These hypotheses are consistent with theories of learning and forgetting. However, it is likely that not all of these covariates will be significantly related to performance. Research Question 3.3: We will classify responses at the end of treatment (learner vs. non-learner) and post-treatment (rememberer vs. forgetter). Then, earlier performance will be analyzed to determine when treatment and post-treatment outcomes can be predicted. This yields empirically based benchmarks for progress and an understanding of the stability of learning and forgetting over time. As with RQ 3.1 and 3.2, we will separate treatment and post-treatment data as well as definition and naming data. Within each dataset, we will classify each child as having a negative or positive outcome based on performance at the last point in the series (i.e., reading 6 for treatment, 12-month post for post-treatment). We will use the accuracy range for the untreated control words to determine the cut-offs for this classification. Then, we will select an appropriate cut-off score at each earlier point during treatment or post-treatment. Because we have decided that the cost of false positives is greater than that of false negatives (see progress report), we will select cutoffs that minimize false positives. At each test point, measures of sensitivity, specificity, and positive/negative likelihood ratios and predictive values will be calculated. We will then determine the earliest point when we can accurately predict treatment and post-treatment outcomes

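### RQ3.2 tests what predicts learning of treated words, but the low-power fallback would read the result as which children benefit from treatment, and no planned term tests that

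*Combined protocol and SAP*

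**What the plan says.** The Research Questions and Hypotheses sections word RQ3.2 as a question of association with learning and forgetting. Under Statistical models, pre-treatment measures are added one at a time to the RQ3.1 growth models "to examine the relationship between these covariates and (a) learning slopes during treatment" and, likewise, forgetting slopes. Those models focus on treated words. The only interaction named is time slope by testing condition.

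The Sample size section gives the design: "Sixty kindergarten children with DLD will participate", and "Children will be randomized to one of the 3 treatment manipulations (see manipulated variables) yielding 20 children per treatment condition". Every child is therefore treated. For each child "definition and naming data will be collected for 30 treated words and 30 control words", on the same occasions. Control words get a similar model for the treatment phase, to separate treatment from maturation, and near-flat trajectories are expected in each condition.

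The Sample size rationale for 3.2 adds a fallback. If power proves insufficient, the significance criterion may be loosened to look for promising moderators. These would need further testing but "would inform our understanding of which children with DLD may benefit from the treatment, addressing the research question".

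**The concern.** A predictor's link to the treated-word slope, in children who all receive treatment, is a prognostic association. A child with stronger language or memory may gain on any word that comes round repeatedly, treated or not. To say that treatment helps some children more than others, the predictor must relate to the difference between treated and untreated learning.

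The fallback claims the second while the model supplies the first. It also says that this addresses the research question, although RQ3.2 as written does not ask who benefits. The label matters because the fallback intends these traits for further testing as the treatment is developed. It would also be attached under a relaxed criterion, so the strongest claim would rest on the weakest evidence. Within-child control words could supply the missing contrast, but no RQ3.2 analysis is stated to use them.

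**Working it through.** **1. What the stated power refers to.** Inputs from the Sample size rationale: N = 60; "Prior research by the team has indicated that correlations between predictors and learning are in the range of .4 and .5"; "Slope reliabilities of .6 and .8 were considered in the specification of the population parameters". Significance level and sidedness are not stated, so two-sided .05 is assumed. The plan says power for predictors of "slopes added to the treatment model will range from .70 to .85".

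Approximation: power = Φ(atanh(r√reliability) × √(N − 3) − 1.96).

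- r = .4, reliability .6: observed r = .310; .320 × 7.550 = 2.419; power .68
- r = .5, reliability .6: observed r = .387; .409 × 7.550 = 3.085; power .87
- r = .4, reliability .8: power .81
- r = .5, reliability .8: power .95

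The stated range lies close to the reliability-.6 results. It cannot be confirmed exactly, because it comes from a Monte Carlo study whose full inputs are not given. It is about what a simple predictor-slope association pooled over 60 children would have, so it is power for prediction and not for effect modification.

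**2. When the two readings diverge.** The documents give no control-slope figures, so these are assumptions. Scale the true treated slope to variance 1 and take r = .45 and reliability .7 (midpoints of the plan's ranges). Control residual slope SD is half the treated residual SD, control slope error SD is .7 of the treated error SD, and residuals are independent. Let f be the predictor's effect on control slopes as a fraction of its effect on treated slopes.

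Variance of treated minus control slope = (.45(1 − f))² + .7975 (treated residual, 1 − .45²) + .4286 (treated error, 1/.7 − 1) + .1994 (control residual, .25 × .7975) + .2100 (control error, .49 × .4286) = (.45(1 − f))² + 1.635.

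Correlation of predictor with the difference = .45(1 − f) / √variance. The implied true predictor-control correlation is .45f / √((.45f)² + .1994).

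| f | Implied predictor-control r | Predictor-difference r | Treated-word test significant | Treated-minus-control test significant |
|---|---|---|---|---|
| 0 | 0 | .332 | about 86% | about 75% |
| ¼ | .24 | .255 | about 86% | about 51% |
| ½ | .45 | .173 | about 86% | about 26% |
| 1 | .71 | 0 | about 86% | 5% |

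The percentages come from simulation. The closed form gives 85% for the treated-word test (observed r = .45√.7 = .376) and 74%, 50%, 26% and 5% for the difference. The treated-word result does not change with f, so it cannot tell these situations apart.

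**3. Cost of the added test at f = 0, same assumptions.**

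| r | Reliability | Treated-word power | Difference power | Loss (points) |
|---|---|---|---|---|
| .4 | .6 | .685 | .554 | 13 |
| .4 | .8 | .814 | .709 | 10.5 |
| .5 | .6 | .873 | .765 | 11 |
| .5 | .8 | .956 | .897 | 6 |

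The loss depends on the control slopes. The next two cases use the step 1 formula, with reliability applied to the difference itself. If control slopes are flat for every child, power is unchanged (.68 to .95). If they vary as much as treated slopes, independently of them and of the predictor, power is .39 to .70. That is a loss of 26 points (.95 − .70, r = .5, reliability .8) to 31 points (.81 − .50, r = .4, reliability .8), but such control slopes would hardly be flat.

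**4. Predictor-by-condition is not a substitute.** It asks who responds to the amount of testing. For one pair of arms (20 v 20) and reliability .6 to .8, power is .22 to .29 for r = .5 v 0, .15 to .19 for .4 v 0, and .09 to .11 for .5 v .25.

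**The case against.** The strongest reply is that the main plan is worded correctly. The research question, hypotheses and model section speak of association, covariates and predictors, and for that question the treated-word test is the right one. The moderator language appears only in a fallback that is hedged and calls for further testing. This stands. A reader might infer that RQ3.2 as a whole will report prognostic traits as moderators; the documents do not support that. The hedging does not mend the fallback itself, since further testing does not correct a label that names a different quantity.

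Second, if control words are flat for each child, the treated-word slope approximates the treatment gain and the planned test approximates moderation. That is also right. But flatness is expected only by condition, and a flat average can hide stronger children rising while others stay at zero. On one reading the RQ3.2 covariates also enter the control-word model. The plan's count of four models, by phase and outcome, makes that uncertain, and a separate control-word model would still not test the difference.

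Third, a reader might take 86% v 5% as the expected rate of false moderator findings. It is not. That row needs a predictor-control correlation of about .7, stronger than the .45 assumed for treated words, and it sits poorly with the flat control trajectories the plan expects. Nothing in the documents suggests that it is likely.

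**Conclusion.** The point holds for the fallback and its interpretation, not for the primary RQ3.2 test. The specified model cannot support a statement about which children benefit, because it contains no treated-against-untreated contrast by predictor. The size is conditional. The two readings nearly agree if control-word growth is unrelated to the predictor (about 86% v 75% significant). They separate steadily as that link grows (51% at a quarter of the treated effect, 26% at half). These figures rest on the assumed control-slope variance and error, independent residuals and two-sided .05; the documents supply none of these. The logical gap does not depend on them. This is an inexpensive improvement to a secondary question, not a flaw that undermines the planned analysis.

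**What to change.** - **Statistical models, RQ3.2:** keep the treated-word predictor x time test as the RQ3.2 test and report it as a predictor of learning.
- **RQ3.2(a):** add a secondary, exploratory predictor x time x word-type (treated v control) test, fitted to both word sets together. State its scale. A Poisson-type link is planned and control counts may be near zero, so report the difference in words gained as well as the log-scale interaction; the two can disagree.
- **Sample size rationale, 3.2:** write *predictors* in place of *key moderators*, and use *moderator* or *benefit* only where the three-way term supports it.
- **RQ3.2(b):** use predictor-of-retention wording only. The plan describes control-word modelling for the treatment phase alone.

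Cost: wording plus one term, using control-word data already scheduled, with no extra children or visits. The term has lower power, by about 6 to 13 points in the main example and more if control slopes vary widely, hence its exploratory status. Before fixing the model, confirm from the attached procedure files how control words are tested in each condition; those details are not in the text reviewed here.
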